### 10.1 Primary Study Endpoints

The difference in average change in SHIM score, between baseline and 12 months post RARP between the membrane and control arms will be assessed as the primary endpoint.

### 10.2 Secondary Endpoints

- Among men with a SHIM greater than or equal to 17 at baseline, we will compare the proportion of men in each group with mild ED or better, defined by a SHIM greater than or equal to 17, at 3, 6, 9 and 12 months post RARP.

- Among men with a SHIM greater than or equal to 17 at baseline, we will compare the proportion of men in each group who are able to achieve an erection sufficient for intercourse more than 50% of the time at 3, 6, 9 and 12 months post RARP.
- Among men with a SHIM greater than or equal to 17 at baseline, we will evaluate the proportion of men in each group who require the use of more invasive erectile aids (intra-cavernosal injection, vacuum pump, or penile prosthesis) at 3, 6, 9, and 12 months post RARP.
- Rates of urinary control as measured by no pads per day at 3, 6, 9, and 12 months.

### **10.3 Safety Parameters**

- Rates of Adverse Events categorized by type, short name, grade, and relationship to treatment using National Cancer Institute Common Terminology Criteria for Adverse Events (NCI CTCAE) version 4.03 criteria
- Rate of recurrence will be assessed and reported at 60 months

### **10.4 Endpoint definitions**

- Potency as measured by well-validated questionnaires: SHIM and EPIC 26. A SHIM greater than or equal to 17 defines mild ED or better
- Urinary continence or control is defined as no pads per day
- Recurrence post-radical prostatectomy defined as a PSA > 0.2 ng/ml on 2 or more consecutive reads or the receipt of any salvage therapy.

### **10.5 Sample size, accrual and study duration**

Exploratory data analyses on 140 men who underwent radical prostatectomy at the University of Miami (between 2008 and 2012) suggests that men typically drop from a mean SHIM score of 19 at baseline down to approximately a score of 9 one-year post radical prostatectomy. Assuming that the control (no membrane) group will experience declines in SHIM scores similar to this historical cohort, with a mean reduction of 10 SHIM points and a standard deviation on the change scores between the observed 8.5 SD and the pessimistic one sided 80% upper confidence limit of 9.8, and allowing one interim analysis at 50% accrual, our study with 70 patients per group can detect, with 80% power, an effect size of 0.335, as shown in Table 10.1 in this section.. (PASS 14 Power Analysis and Sample Size Software (2015). NCSS, LLC. Kaysville, Utah, USA, [ncss.com/software/pass/](http://ncss.com/software/pass/)) For instance, our proposed study with 70 per group has 80% power to detect a difference of 2.68, between sexual function mean reductions of 10 and 7.32 in treatment groups without and with the membrane respectively, assuming a common standard deviation of 8. As

expected with larger standard deviations only larger absolute differences can be detected with 80% power (See rows 2 and 3 in Table 10.1).

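### Section 10.5: the upper SD limit of 9.8 cannot be reproduced from 140 men, and the 80%-power example uses an SD of 8, below the observed 8.5, so it is too favourable

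*Combined protocol and SAP*

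**What the plan says.** Section 10.5 cites one data source: "Exploratory data analyses on 140 men who underwent radical prostatectomy" at the trial centre. It assumes a control arm "with a mean reduction of 10 SHIM points" and an SD of the change scores "between the observed 8.5 SD and the pessimistic one sided 80% upper confidence limit of 9.8". It does not say how many of the 140 men had SHIM scores at both baseline and one year, or how the limit was calculated.

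The section then claims that "our study with 70 patients per group can detect, with 80% power, an effect size of 0.335". Its worked example says that the trial "has 80% power to detect a difference of 2.68, between sexual function mean reductions of 10 and 7.32" in the two arms, "assuming a common standard deviation of 8".

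Table 10.1 gives rows for SDs of 8, 9 and 10. The detectable differences are 3.80, 4.27 and 4.74 points, with effect sizes of 0.475, 0.474 and 0.474, all at 80% power with 70 per arm. The text refers the reader to rows 2 and 3 for larger SDs. No row uses 8.5 or 9.8.

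**The concern.** Two things do not fit. First, 140 men estimate an SD quite precisely, so an 80% upper limit 1.3 points above 8.5 is too far away. Either the n behind the SD is much smaller than 140, or the confidence level or the limit is misreported. Second, having set a range that starts at the observed 8.5, the plan illustrates its power at 8 and gives no reason.

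The statement of what 70 per arm can detect on the primary endpoint is at stake. A reader who relies on the written example will think the trial can detect a smaller difference than it can at the SD actually observed. If only a small subset had paired scores, the SD and the mean fall of 10 points would also rest on less evidence than a cohort of 140 suggests.

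**Working it through.** **Inputs.** From Section 10.5: observed SD s = 8.5, cohort of 140, stated limit 9.8 at one-sided 80%, example SD 8 with difference 2.68. From Table 10.1: 70 per arm and total alpha 0.05. From Section 10.7.3: nominal levels 0.003 (interim) and 0.049 (final), O'Brien-Fleming spending, one look at half the patients. Assumptions: two-sided testing (this reproduces the table), all 70 per arm contribute a 12-month score, and change scores are roughly normal.

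**1. The upper limit.** Upper limit = s × √[(n − 1) / χ²(0.20; n − 1)].

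- n = 140: χ²(0.20; 139) ≈ 124.8, so 8.5 × √(139 / 124.8) = **8.97**. The large-sample form, s × [1 + 0.8416 / √(2 × 139)], gives 8.93. Letting 8.5 stand for anything from 8.45 to 8.55 gives 8.92 to 9.02.
- Other confidence levels with n = 140: 90% gives 9.22, 95% gives 9.44, 97.5% gives 9.63 and 99% gives 9.87. Solving for 9.8: 139 × (8.5 / 9.8)² = 104.6, which a χ² on 139 df exceeds with probability 0.987. So 9.8 is about a 98.7% limit.
- Other n at 80%: n = 70 gives 9.20; n = 25 gives 8.5 × √(24 / 18.06) = 9.80. Values of n from 24 to 26 round to 9.8 (23 to 28 if 8.5 is itself rounded).

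No form tried at 80% confidence gives 9.8 from 140 men.

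**2. Reproducing Table 10.1.** With two looks at nominal 0.00305 and 0.049, the overall two-sided alpha is 0.050. With 70 per arm the expected final z is d × √(70 / 2), and the two looks have correlation √0.5. Power is 0.801 at d = 0.475 and 0.799 at d = 0.474, so the table's rows are right. Power of exactly 80% is at d = 0.4744.

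**3. Detectable difference (0.4744 × SD) at 80% power.** The last column is illustrative: it gives the power for row 1's difference of 3.80 if the SD is larger than 8.

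| SD | Detectable difference | Power for 3.80 points |
|---|---|---|
| 8 (example, row 1) | 3.80 | 80% |
| 8.5 (observed) | 4.03 | 75% |
| 8.97 (80% limit, n = 140) | 4.26 | 71% |
| 9.8 (stated limit) | 4.65 | 63% |

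**4. The example as written.** 2.68 / 8 = 0.335. Two-look power with 70 per arm is 0.507. At SD 8.5 the same 2.68 points has power 0.461. For 80% power, an effect size of 0.335 needs about 140 per arm.

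**5. Splitting the gap.** From the text's 2.68 to the 4.03 supported at SD 8.5 is 1.35 points. The effect size of 0.335 accounts for 3.80 − 2.68 = 1.12, and the choice of SD 8 accounts for 4.03 − 3.80 = 0.23.

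**The case against.** A reader might infer that the planning SD range is simply wrong. The documents do not support that. They say that analyses were done on 140 men, not that 140 men had paired scores. With about 25 pairs, 9.8 would be a correct 80% limit. Nor can one conclude that only 25 had pairs, because a slip in the confidence level or in the figure explains the mismatch equally well. What can be said is that the limit is not reproducible from what is stated.

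A reader might also infer that 9.8 inflates the power. It does the opposite: too large an upper limit makes the pessimistic case more pessimistic, and 70 per arm was not derived from it.

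Table 10.1 also gives substantial cover. Its SDs of 8, 9 and 10 bracket 8.5 to 9.8. Row 2 (SD 9, 4.27 points) nearly coincides with the limit for 140 men (8.97, 4.26 points), and row 3 is harsher than 9.8. The effect size hardly changes with the SD, so a reader can scale it to 8.5. This stands, and it is a reason to keep rows 2 and 3.

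Finally, 3.80 is an output of the table and not a declared target, so a fall in power to 75% or 63% is not a loss against a prespecified effect. That also stands. The SD choice alone moves the detectable difference by 0.23 points, and the text's 0.335 and 2.68 are the larger error. Neither point rescues the example, which is presented as the trial's 80%-power case, uses an SD the preceding sentence excludes, and has about 51% power.

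**Conclusion.** The point holds in a limited form. The stated 80% limit of 9.8 does not follow from an SD of 8.5 in 140 men, for whom it would be 8.97; the n and method behind it are missing. The 80%-power example is too favourable. At the observed SD the detectable difference is 4.03 points, not 3.80 and not 2.68, and 2.68 points has 51% power at SD 8 and 46% at 8.5.

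These figures assume a two-sided overall alpha of 0.05 with the two O'Brien-Fleming looks, equal SDs in the arms, and 12-month scores from all 70 per arm. The 8.97 further assumes 140 paired scores. Nothing here shows that the sample size, the randomisation, the analysis or the stopping boundaries must change. It is a correction to the stated justification and should be made.

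**What to change.** In Section 10.5:

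- State how many of the 140 men had SHIM scores at both baseline and one year, and how the upper limit was obtained. Then correct whichever element is wrong: the limit (8.97 if all 140 had pairs), its confidence level, or the n.
- Base the written example on SD 8.5. Replace the effect size of 0.335 and the difference of 2.68 (10 against 7.32) with an effect size of 0.474 and a difference of 4.03 points (10 − 4.03 = 5.97, so 10 against 5.97) at 80% power. Changing only the SD, or only the 2.68, would leave the other error in place.
- Add a row for SD 8.5 to Table 10.1. Keep the SD 9 and SD 10 rows as sensitivity cases, since removing them would narrow the range shown. Keep the SD 8 row only if it is labelled optimistic.

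The cost is a few restated figures and a less favourable detectable difference. The sample size stays at 70 per arm.

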#### **4.1 Accrual goal**

70 men will be allocated to each arm. The rationale for this number is provided in the sample size section of the statistical analysis (Section 10.5)

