## 10. STATISTICAL CONSIDERATIONS

This is a blinded two-arm randomized phase 2 trial. Patients will be randomized in a ratio 1:1 to study arms, the experimental Arm I (membrane placement) and control Arm II (no membrane placement, standard of care surgery), using a permuted block design stratified by baseline SHIM score (<17 vs. >=17), and use of ANY erectile aids (Yes vs. No) in the last 3 months.

All analyses will be performed as an intention to treat and as per Protocol. Although there is no data to suggest an increased risk of any potential adverse effects with placement of a sling, we will monitor adverse events as per section 10.7.2. An interim analysis of the primary efficacy endpoint, change in SHIM score, will be performed as part of the analysis plan as described in section 10.7.3..

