**Table 10.1: Estimated effect size that can be detect with our proposed study with 140 total patients (70 per arm)**

Power	N1	N2	N	Mean1	Mean2	S1	S2	Alpha	Effect size	Alpha
0.80	70	70	140	10	6.20	8	8	3.80	0.475	0.05
0.80	70	70	140	10	5.73	9	9	4.27	0.474	0.05
0.80	70	70	140	10	5.26	10	10	4.74	0.474	0.05

Effect size = (Mean 1 – Mean 2) / S (standardized mean difference).

Note: These results assume that 2 sequential z-test are made using the O'Brien-Fleming spending function to determine the test boundaries. The study will stop early at 50% accrual, for either futility or superiority, if the interim analysis result is significance at  $p < 0.03$ . The nominal significance level at the second test is 0.049. (PASS 14).

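### Section 10.5 claims 80% power at 70 per arm for an effect size of 0.335 (2.68 SHIM points); the design has about 51% power for that, and Table 10.1 gives 0.475 (3.80 points)

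*Combined protocol and SAP*

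**What the plan says.** Section 4.1 sets the sample size ("70 men will be allocated to each arm") and refers to Section 10.5 for the reason. Section 10 confirms equal allocation: "Patients will be randomized in a ratio 1:1 to study arms".

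Section 10.5 then states that "our study with 70 patients per group can detect, with 80% power, an effect size of 0.335, as shown in Table 10.1". Its worked example is that the study "has 80% power to detect a difference of 2.68, between sexual function mean reductions of 10 and 7.32", "assuming a common standard deviation of 8". The sentence before the example assumes a "standard deviation on the change scores between the observed 8.5 SD and the pessimistic one sided 80% upper confidence limit of 9.8".

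Table 10.1 is titled "Estimated effect size that can be detect with our proposed study with 140 total patients (70 per arm"). Each of its rows has 70 per arm, power 0.80 and alpha 0.05:

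| SD | Mean reductions | Difference | Effect size |
|---|---|---|---|
| 8 | 10 vs 6.20 | 3.80 | 0.475 |
| 9 | 10 vs 5.73 | 4.27 | 0.474 |
| 10 | 10 vs 5.26 | 4.74 | 0.474 |

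The table defines effect size as the difference in means divided by the SD. Its note and Section 10.7.3 describe two sequential z-tests with O'Brien-Fleming spending and one interim look at 50%. Section 10.7.3 gives nominal levels of 0.003 (interim) and 0.049 (final).

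**The concern.** The text cites the table as its source, yet 0.335 appears nowhere in the table. The metric is the same in both places (2.68 / 8 = 0.335 and 3.80 / 8 = 0.475), and so are the sample size, power, SD and alpha. Both figures cannot be right.

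This is the power statement for the primary endpoint and the only justification given for 140 men. If the text is wrong, anyone relying on it, including those reading a null result, could take the trial to have had a good chance of finding a 2.68-point benefit when it did not.

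Two lesser points sit in the same paragraph. The example uses SD 8, which is below the observed 8.5 and outside the 8.5 to 9.8 range assumed one sentence earlier. The 9.8 upper limit also looks too high if all 140 historical men contributed a change score.

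**Working it through.** **Inputs.** n = 70 per arm (Section 4.1); 1:1 allocation (Section 10); one look at half the information, nominal levels 0.003 and 0.049 (Section 10.7.3); z-tests (note to Table 10.1); SDs of 8, 9 and 10 (Table 10.1) and of 8.5 and 9.8 (Section 10.5). Sidedness is not stated, so two-sided is taken first and checked below.

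**Method.** For effect size d, the final z-statistic has mean d × √(n/2) and the interim one has mean d × √(n/2) × √0.5; their correlation is √0.5. The critical values are 2.968 (interim) and 1.969 (final). Power is one minus the bivariate normal probability of staying inside both pairs of limits. With d = 0 this gives an overall alpha of 0.0500, as the plan intends.

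**Reproducing Table 10.1.** At n = 70, power reaches 80% at d = 0.4744. Multiplying by the SD:

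- SD 8: 0.4744 × 8 = 3.80
- SD 9: 0.4744 × 9 = 4.27
- SD 10: 0.4744 × 10 = 4.74

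All three rows reproduce. One-sided testing at 0.05 would give about 88% power for these rows, so the table was computed two-sided.

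**The text figure.** For d = 0.335, d × √(n/2) = 0.335 × √35 = 1.982. A fixed two-sided test has power of about Φ(1.982 − 1.960) = Φ(0.022) = 0.509. The two-look design gives 0.507. Other readings also fall short of 80%:

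| Reading | Power for d = 0.335 at 70 per arm |
|---|---|
| Two looks, 0.003 / 0.049, two-sided | 50.7% |
| Fixed z-test, two-sided | 50.9% |
| Fixed t-test, two-sided | 50.3% |
| Two looks, interim level 0.03 as printed under Table 10.1 | 52.9% |
| One-sided 0.05 | 63% |

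**Where 0.335 may come from.** Under the two-look design, 80% power for d = 0.335 needs 140.4 men per arm, and 140 per arm detects 0.3355. Since 140 is the trial's total, the total may have been entered as the per-arm number. This is an inference, and the finding does not depend on it.

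**At the plan's own SDs**, two-look and unadjusted:

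| SD | Power for 2.68 points | Difference detectable with 80% power |
|---|---|---|
| 8 | 51% | 3.80 |
| 8.5 | 46% | 4.03 |
| 9 | 42% | 4.27 |
| 9.8 | 36% | 4.65 |

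**The 9.8 limit.** Assume that all 140 historical men gave a change score and that the usual chi-square interval was used. The one-sided 80% upper limit is then 8.5 × √(139 / χ²(0.20; 139)) = 8.5 × √(139 / 124.8) = 8.97. A limit of 9.8 corresponds to about 25 men: the same formula with n = 25 gives 9.80.

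**The case against.** The contradiction cannot be explained away as a misread digit, because 0.335, 2.68 and 7.32 agree with each other. The best arguments on the other side concern its weight.

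- *The correct figures are directly below, and no trial procedure uses 0.335.* True, and 140 men is consistent with the table. This makes the repair cheap, but the sentence that states the power is still wrong.
- *The primary analysis will report a 95% confidence interval, so a null result would be judged on that.* This is fair. It limits the harm to readers who rely on the planned power, so the consequence is a risk of misreading, not a certainty.
- *The regression in Section 10.6 adjusts for baseline SHIM, age and oral aids, which could raise power.* It could. To reach 80% for 2.68 points at SD 8, the residual SD would have to fall by the factor 0.335 / 0.475 = 0.705. That needs a correlation of √(1 − 0.705²) ≈ 0.71 between covariates and change score, or about half the variance explained. The documents give no such figure, and the text attributes its number to a table built on the unadjusted SD.
- *SD 8 is only an instance, and the table's SDs of 8, 9 and 10 bracket 8.5 to 9.8.* This stands in part. SD 8 is not an arithmetic error, but it is more favourable than the plan's own assumption, and no row shows the observed value.
- *The 9.8 limit may be correct.* This stands. It depends on how many men had paired scores and on the interval method, and neither is stated. The point is a query.
- *Neither 2.68 nor 3.80 is justified as the target difference.* Also true. Keeping 140 men assumes that the table represents the intended design.

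**Conclusion.** The concern holds. The power statement in the text of Section 10.5 is wrong, and Table 10.1, which it cites, is numerically right. With 70 men per arm the trial has about 51% power for 2.68 points at SD 8, not 80%, and about 46% at the observed SD of 8.5. A true benefit of that size would therefore be missed about half the time, or more often than not at the observed SD. The detectable difference is understated by 3.80 − 2.68 = 1.12 points at SD 8, and by 4.03 − 2.68 = 1.35 points at SD 8.5.

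These figures are for an unadjusted two-sided comparison with complete 12-month scores. Two-sidedness is inferred from the table. Section 10.5 makes no allowance for missing scores, which would lower power further.

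**What to change.** In Section 10.5:

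1. Replace 0.335 with 0.475, so that text and table agree.
2. Replace the worked example with the design's figures at the assumed SDs: about 4.0 points at SD 8.5 (mean reductions of 10 and about 6.0) and about 4.65 points at SD 9.8.
3. State that power for 2.68 points is about 51% at SD 8 and 46% at SD 8.5, for an unadjusted two-sided test.
4. Add a row to Table 10.1 for SD 8.5 (difference about 4.03, effect size 0.474). While editing, relabel the difference column, which is headed as a second alpha column, and reconcile the interim level in the table note (0.03) with Section 10.7.3 (0.003).
5. State how many historical men had paired scores behind the 9.8 limit and the method used, or correct the limit.

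The sample size stays at 140, provided the sponsor confirms that the table states the intended target. If 2.68 points was the real target, wording alone will not do, because about 140 men per arm would be needed. Otherwise the cost is a text and table edit, with no effect on conduct. The price is a less favourable claim: about 4 points instead of about 2.7.

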### **5.7 Cancellation Guidelines**

The following are reasons for withdrawal of subjects from the study:

- A subject does not meet the eligibility criteria, (the subject will be considered a screen failure).
- A subject withdraws consent,
- A subject dies during protocol participation or
- A study investigator decides the subject should be withdrawn from the study (e.g. subject non-compliance)

Regardless of reason for withdrawal, once a patient has been randomized to an arm, an intention to treat analysis will be performed.

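### Table 10.1's 80% power uses all 70 men randomised per arm and makes no allowance for a missing 12-month SHIM; 10–20% loss would bring it to about 76–71%

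*Combined protocol and SAP*

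**What the plan says.** **Numbers randomised.** Section 4.1 (Accrual goal): "70 men will be allocated to each arm". It refers to Section 10.5 for the reason.

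**Numbers in the power calculation.** All three rows of Table 10.1 use 70 and 70, 140 in total, for 80% power at effect sizes of 0.475, 0.474 and 0.474 (3.80, 4.27 and 4.74 points at SD 8, 9 and 10). The prose of Section 10.5 also uses 70 per group, but gives a different effect: the study "can detect, with 80% power, an effect size of 0.335, as shown in Table 10.1". Its example says "our proposed study with 70 per group has 80% power" "to detect a difference of 2.68, between sexual function mean reductions of 10 and 7.32", "assuming a common standard deviation of 8".

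**What the endpoint needs.** Section 10.1 defines the primary endpoint as the between-arm difference in mean SHIM change from baseline to 12 months. Section 10.7.1 places the interim analysis at the first 50% of study patients. Section 10.7.3 describes it as 70 men, about 35 per arm, already assessed at one year. Half of the trial is thus 70 men with a 12-month score, so the design counts all 140 as assessed.

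**What is foreseen about loss.** Section 5.7 begins "The following are reasons for withdrawal of subjects from the study" and lists withdrawn consent, death and an investigator's decision, besides ineligibility. Sections 5.7 and 7.3 answer with intention to treat, and Section 7.3 keeps men who discontinue in follow-up for clinical data. No expected loss rate, inflation of the sample size or method for a missing 12-month SHIM appears in the documents.

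**The concern.** Intention to treat keeps every randomised man in his arm but does not supply a score that was never recorded. If the number randomised equals the number in the power calculation, each missing 12-month SHIM comes straight out of the planned information.

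What is at stake is how the result is read. Sections 1.3 and 1.4 present the trial as the randomised test of a technique already in wide use on observational evidence. A null result will be judged against the effect the trial could have detected, and a power figure that presumes complete data makes that effect look smaller than it was.

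**Working it through.** **Inputs**
- n = 70 per arm (Section 4.1; Table 10.1).
- Row 1 of Table 10.1: difference 10 − 6.20 = 3.80, SD 8, so d = 3.80/8 = 0.475.
- Two looks, at 50% and 100%, with O'Brien-Fleming spending and total alpha 0.05 (Section 10.7.3). The nominal levels there are 0.003 and 0.049. I used 0.00305 and 0.049 two-sided, which together give a total of 0.0500. Sidedness is not stated; two-sided reproduces the table.
- Loss rates of 5%, 10% and 20%: **assumptions**, since the documents give none.

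**Formula.** With n men per arm assessed, θ = d·√(n/2). The interim and final statistics are bivariate normal with means θ·√0.5 and θ, unit variances and correlation √0.5. The critical values are c₁ = 2.963 and c₂ = 1.969.

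Power = 1 − P(|Z₁| < c₁ and |Z₂| < c₂)

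**Step 1: reproduce Table 10.1.** For row 1, θ = 0.475 × √35 = 0.475 × 5.916 = 2.810. The final look alone gives Φ(2.810 − 1.969) = 80.0%; both looks give 80.1%. Rows 2 and 3 give 80.0% and 79.9%. Solving row 1 for n gives 69.8 men per arm, so the table is right at 70 and has no slack.

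**Step 2: apply loss to row 1.**

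| Assumed loss | Men per arm with 12-month SHIM | θ | Two-look power |
|---|---|---|---|
| 0% | 70 | 2.810 | 80.1% |
| 5% | 66.5 | 2.739 | 78.0% |
| 10% | 63 | 2.666 | 75.8% |
| 20% | 56 | 2.513 | 70.8% |

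The decline is gradual: 79.5% at 69 per arm and 78.4% at 67, or about 0.6 points per man lost per arm.

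**Step 3: effect detectable with 80% power.** This scales as 0.4744/√(1 − loss).

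| Assumed loss | Effect size | Points at SD 8 | SD 9 | SD 10 |
|---|---|---|---|---|
| 0% | 0.474 | 3.80 | 4.27 | 4.74 |
| 5% | 0.487 | 3.89 | 4.38 | 4.87 |
| 10% | 0.500 | 4.00 | 4.50 | 5.00 |
| 20% | 0.530 | 4.24 | 4.77 | 5.30 |

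**Step 4: the prose example.** Here d = 2.68/8 = 0.335 and θ = 0.335 × 5.916 = 1.982. Two-look power at 70 per arm with complete data is 50.7%. An effect size of 0.335 needs about 140 per arm for 80%. The prose figure therefore matches 140 per group, whereas the trial has 140 in total.

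**Step 5: what covariate adjustment could return.** Section 10.6 plans a linear model with baseline SHIM, age and use of oral aids. If the covariates explain a share R² of the variance of the change score, the residual SD is 8·√(1 − R²). Restoring 80% at 63 per arm needs a residual SD of 7.60, so R² = 1 − (7.60/8)² ≈ 0.10. At 56 per arm it needs 7.16, so R² ≈ 0.20. The documents give no R².

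**The case against.** **Any loss makes the stated power false.** A reader might infer this, but it is too strong. Three men lost per arm leaves row 1 at 78.4%, within two points of a planning figure that itself rests on an assumed SD. The SD matters as much: Section 10.5 puts it "between the observed 8.5 SD and the pessimistic one sided 80% upper confidence limit of 9.8", and 3.80 points at 70 per arm with no loss has 75.2% power at 8.5 and 62.9% at 9.8.

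**Complete follow-up would deliver the 80% in the prose.** A reader might infer this too. It would not: the 2.68-point example has about 51% power with every man assessed. That fault is a conflict between the prose and Table 10.1, and attrition does not cause it. Adding that 80% applies to complete data, without correcting the example, would put a further false statement into Section 10.5.

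**The planned model may make up the loss.** This stands as a possibility. Table 10.1 is an unadjusted z-test, and a modest R² would offset 10% loss. But the plan states no R² and claims no such gain, so it cannot be counted on.

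**Withdrawal is not a missing outcome.** This stands in part. One of the reasons in Section 5.7 is ineligibility, handled as screen failure, and Section 7.3 continues follow-up after discontinuation. Neither section guarantees a 12-month SHIM from a man who withdraws consent or dies.

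**The confidence interval will show the precision achieved.** True: Section 10.6 reports the difference with a 95% CI, which limits the harm from a misread null result. It does not correct the design statement.

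**Conclusion.** The point holds as an omission. Table 10.1 is arithmetically right, but its unadjusted 80% at an effect size of about 0.474 requires about 70 men per arm assessed at 12 months, which is everyone randomised. At assumed losses of 5%, 10% and 20% the power is about 78%, 76% and 71%.

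These figures rest on assumed loss rates, equal loss in both arms, an analysis of observed scores without covariate adjustment, and the interim look at half the information. Keeping the interim at 35 men per arm when fewer than 70 are assessed changes the powers by less than 0.1 point. The documents do not show that loss will occur at any particular rate, nor that the adjusted analysis will fall short of 80%.

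The mismatch between 0.335 in the prose and 0.475 in the table is a separate and larger error in the same section, and has to be corrected together with this one.

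**What to change.** In one edit to Section 10.5 and Table 10.1:

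1. Restate the table as the difference detectable with 80% power for 70 men **randomised** per arm, at 0, 5, 10 and 20% missing 12-month SHIM (effect sizes 0.474, 0.487, 0.500 and 0.530, with the points at each SD as in the second table of the working).
2. Say that the figures are unadjusted, that the loss rates are planning assumptions, and that adjustment for baseline SHIM and the other covariates may recover some power.
3. Replace 0.335 and the 2.68-point example with figures that agree with the table: 0.475 and 3.80 points (mean reductions of 10 and 6.20) at SD 8. Only then add that 80% refers to complete 12-month data.

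No additional patients and no change in conduct are needed. The cost is a slightly less favourable stated figure.
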